5.4 TDSMC and Dose Selection

A Trial Data and Safety Monitoring Committee (TDSMC), consisting of all investigators (or their designee), the Chief Investigator (CI) and Sponsor scientific representatives will be constituted. Further details of the composition and function of the TDSMC are contained in a separate TDSMC charter.

Dose Escalation Stage

The TDSMC will review available safety, PK, PD, and clinical data at the completion of each dose level cohort and make a recommendation to the Sponsor as to whether escalation to the next CRM recommended dose level should occur.

The TDSMC may also recommend increasing the number of patients at specific tolerable dose levels, to obtain further information to aid dose selection or evaluation of doses which are intermediate to the pre-specified dose levels in order to further characterise the relationship between dose level and emergent toxicities.

In the event of sufficiently compelling pharmacodynamic or clinical efficacy (with an acceptable safety profile) at a particular dose level, the TDSMC may recommend that particular dose level for the expansion stage, prior to the determination of a maximum tolerated dose, or completion of the scheduled range of dose levels. In this situation the TDSMC will decide whether the dose escalation stage should continue in parallel with the expansion stage, in order to further define the safety and tolerability of DTP3 up to a maximum tolerated dose (although any such findings will **not** lead to a reappraisal of the already determined RP2D level for the dose expansion stage).

Dose Expansion Stage

Ongoing safety data will be reviewed by the TDSMC during the expansion stage, with a frequency of no less than every seven patients (across both cohorts) who have been treated for at least 8 weeks with DTP3 (*i.e.* 2 cycles of treatment). Dose delays due to DTP3 related toxicity are included as part of the 8-week period [*i.e* if there is a dose delay during the 8-week period, a patient will still be reviewed for safety even though they may not have received two complete cycles of DTP3].

5.5 Patient Withdrawal and Replacement

All patients should be treated until disease progression or unacceptable toxicity, whichever occurs first.

During the dose escalation stage, to be **DLT evaluable**, a patient must have received at least 10 of the 12 scheduled doses of DTP3 during Cycle 1 of treatment (in the absence of a DLT having interrupted DTP3 dosing). Non-evaluable patients will be replaced for DLT estimation purposes but may remain in the study.

During the dose expansion stage, patients who are withdrawn for reasons of disease progression and/or unacceptable toxicity will not be replaced. Patient who are not response evaluable may be replaced, after discussion with the medical monitor.

5.6 Dispensing and Accountability

DTP3 will be packaged, labelled, stored, and distributed by Curia ([name]) to each trial site. DTP3 will be provided to individual site pharmacies in single-use glass vials containing 4 mL of DTP3 at a concentration of 80 mg/mL. The pharmacy will be required to dispense DTP3 into infusion bags of 0.9% saline, based on dose and patient weight (details will be provided in the DTP3 Pharmacy Guidelines Document). The individual site pharmacy will be responsible for accountability and destruction of the drug at their site, as detailed in the DTP3 Pharmacy Guidelines document.

5.7 Dose Modification

Dose Escalation Stage Only

- No dose reductions are permitted for any patient during the DLT evaluation period [Cycle 1 of DTP3).
- Patients experiencing a DLT may remain in the study at the originally assigned dose of DTP3 or a lower dose according to investigator judgement.

Patients initially entered into the study at a DTP3 dose level lower than the one currently being evaluated may increase their DTP3 dose level [provided they have not experienced a DLT during the DLT evaluation period] by one dose level increment per cycle, at the end of each cycle of treatment, at the discretion of the investigator, provided the DTP3 dose remains at least one level below the highest dose currently being evaluated **Dose Escalation and Expansion Stage**

- Up to **three** dose level reductions are permitted in the event of DTP3 related toxicity, at the discretion of the investigator.
- During the **dose escalation stage**, [for patients who have completed the initial DLT evaluation period] each dose reduction should be to the immediately preceding dose level specified in the DTP3 dose level escalation range [*e.g.* 20mg/kg reduced to 16mg/kg; 16mg/kg reduced to 12mg/kg *etc*]
- For the **dose expansion stage**, the TDSMC will specify a dose reduction algorithm at the time the RP2D level is determined, taking account of the actual RP2D level and the pattern of toxicities seen at lower dose levels during the dose escalation stage.
- Dose reductions are permitted for the following toxicities if they are considered clinically relevant by the investigator:
 - Any Grade 4 adverse event not resolving to at least Grade 3 within 48 hr
 - Any Grade 3 adverse event not resolving to at least Grade 2 within 14 days
 - Any dose delay greater than 7 days
- Any potential dose reduction must be discussed in advance with the Medical Monitor and (if judged appropriate by the investigator and medical monitor) the Chief Investigator too.
- If a dose level is reduced, it may be increased again (to the immediately preceding dose level), at the discretion of the investigator, if there is complete resolution of the original toxicity leading to the dose reduction.

• Dose delays of up to 14 days are permitted for the resolution of DTP3 related toxicity. Patients requiring a dose delay greater than 14 days should be withdrawn from the study. Dose delays of greater than 14 days for reasons other than toxicity (*e.g.* logistical ones) must be discussed with and approved by the medical monitor.

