4.3.1 Withdrawal of treatment

Study treatment may be withdrawn by the investigator for any reason judged to be in the patient's best interests.

Typical criteria for stopping therapy would include (but not be limited to):

- Unacceptable (drug related) toxicity
- Clinical reasons not related to DTP3
- Evidence of disease progression
- Symptomatic deterioration
- Pregnancy
- Withdrawal of patient consent for further treatment

Withdrawal of treatment is **not** the same as withdrawal from the study and all patients stopping therapy should be encouraged to continue with protocol specified follow-up procedures.

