4.3.2 Withdrawal from study

The investigator must make every reasonable effort to keep each patient on study for the whole duration of the trial. However, if the investigator removes a patient from the study or if the patient declines further participation, final off-study assessments should be performed before the start of any alternate non-protocol therapeutic intervention. All the results, evaluations and observations, together with a description of the reasons for withdrawal, must be recorded in the medical records and the electronic case report form (eCRF).

The following are recognised reasons for the investigator to withdraw a patient from the study:

- Withdrawal of patient consent for further study participation
- Serious violation of the study protocol (including persistent patient attendance failure AND/OR persistent non-compliance)
- Sponsor's decision to terminate the study
- Clinical reasons not related to DTP3
- Lost to follow up
- Death

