7.7 Follow Up

All patients who do not have disease progression at the time of ceasing DTP3 treatment will be followed, through routinely scheduled clinic visits for disease progression [according to the schedule in 7.5 above] and survival for a period of six months after the last patient has been recruited into the study.

Patients with disease progression at the time of ceasing DTP3 treatment will be followed up through routinely scheduled clinic visits for subsequent anti-cancer therapies and survival.

Patients' disease progression and survival status should be followed up a minimum of every 6 months, but ideally every 3-4 months through their attendance at routine clinic appointments.

Patients not being actively followed in the clinic will be contacted (or *via* a family member as appropriate) at approximately 2-3 monthly intervals to assess survival status.

Every effort should be made to follow-up patients who have entered the trial. It is the responsibility of the investigator at site to ensure that the follow-up data required by the protocol are collected and reported.

After the study has completed and final results are available, investigators may share these at the request of individual patients.

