7.8 Trial Closure

The trial will be declared closed when either i) the last surviving patient either dies or ii) is withdrawn from the trial, or iii) six months after the last patient has been recruited into the study or iv) the Sponsor decides to terminate the study, whichever occurs first.

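### Section 5.7 and the synopsis withdraw patients with a toxicity delay over 14 days from the study, against Sections 4.3.1, 4.3.2 and 7.7; read literally, this could informatively censor PFS, EFS, DOR and OS

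*Protocol*

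**What the plan says.** Protocol Section 5.7 (Dose Modification) first states: "Dose delays of up to 14 days are permitted for the resolution of DTP3 related toxicity". It continues: "Patients requiring a dose delay greater than 14 days should be withdrawn from the study". Longer delays for other reasons, such as logistics, are handled separately and "must be discussed with and approved by the medical monitor". The withdrawal sentence therefore concerns patients whose drug toxicity has not resolved. The Dose Modification part of the Study Summary carries the same sentence, and the rule covers both the escalation and the expansion stage.

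Elsewhere the protocol says:

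- **Section 4.3.1 (Withdrawal of treatment)** lists unacceptable drug-related toxicity among the typical reasons to stop therapy. It states that stopping treatment differs from leaving the study, and that "all patients stopping therapy should be encouraged to continue with protocol specified follow-up procedures".
- **Section 4.3.2 (Withdrawal from study)** asks investigators to make every reasonable effort to keep patients on study. It lists six recognised reasons for withdrawal. The only clinical one is "Clinical reasons not related to DTP3".
- **Section 7.7 (Follow Up)** provides that "All patients who do not have disease progression at the time of ceasing DTP3 treatment will be followed", for both progression and survival. Patients who stop with progression are followed for later therapy and survival.

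**The concern.** Section 5.7 is where a site looks when toxicity persists, and the synopsis confirms what it finds there. Taken at face value, the instruction removes from the study patients whom three other sections keep in it.

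PFS, EFS, DOR and OS are analysed by Kaplan-Meier (Section 8.3). The method assumes that patients censored at a given time have the same later risk as those who stay under observation. Patients taken off because drug toxicity lasts beyond 14 days are a selected group and may have a worse outlook. If so, ending their follow-up biases the curves upwards. Data never collected cannot be recovered later by a censoring rule in a SAP. With seven centres, sites could also apply the sentence differently.

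**Working it through.** **Step 1: does the text conflict?** For a patient with DTP3-related toxicity that needs a delay of more than 14 days and no progression:

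| Protocol place | Leaves treatment? | Leaves the study? |
|---|---|---|
| 5.7 and synopsis | Yes | Yes, as written |
| 4.3.1 | Yes (drug toxicity) | No; continues follow-up |
| 4.3.2 | Not addressed | No recognised reason applies |
| 7.7 | Yes (ceased DTP3) | No; followed for progression and survival |

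No section reconciles the first row with the others.

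**Step 2: does study withdrawal end follow-up?** The protocol does not say so in one sentence, but its wording points that way. Section 4.3.1 contrasts stopping treatment, where follow-up continues, with leaving the study. Section 4.3.2 closes a study withdrawal with last assessments: "final off-study assessments should be performed before the start of any alternate non-protocol therapeutic intervention". Section 7.8 sets withdrawal beside death in its closure condition: "the last surviving patient either dies or ii) is withdrawn from the trial".

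**Step 3: how large could the effect be on OS?** The protocol gives no expected rate of such delays, so this is an illustration.

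Inputs from the protocol:
- 24 patients per expansion cohort (Section 8.1).
- Median OS of about 6 months in DLBCL after failure of an initial salvage regimen (Section 1.1).

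Assumptions:
- Exponential survival.
- n = 1 or 4 patients withdrawn at month 2.
- Hazard ratio h = 1, 2 or 3 for them afterwards, relative to the others.

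Calculation:
- Alive at month 2: S(2) = 2^(−2/6) = 0.794, and 24 × 0.794 = 19.05, so about 19 patients.
- Fraction withdrawn: f = n/19.05, which is 0.052 for n = 1 and 0.210 for n = 4.
- Kaplan-Meier estimate with these patients censored: 0.794 × 2^(−4/6) = 0.794 × 0.630 = 0.500.
- True value: S(6) = 0.794 × [(1 − f) × 2^(−4/6) + f × 2^(−4h/6)].

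| n | h | True S(6) | Overstatement (points) |
|---|---|---|---|
| 1 | 1 | 0.500 | 0 |
| 1 | 2 | 0.490 | 1.0 |
| 1 | 3 | 0.484 | 1.6 |
| 4 | 1 | 0.500 | 0 |
| 4 | 2 | 0.461 | 3.9 |
| 4 | 3 | 0.437 | 6.3 |

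For scale, the standard error at 50% with 24 patients is √(0.25/24) = 0.102, or about 10 points.

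**Step 4: cross-check on PFS.** A simulation used exponential PFS with a median of 5 months for patients not withdrawn (the protocol's approximate figure for this MM population, Section 1.1). A fraction f was censored at month 2, with a hazard k times that of the others; f, k and the timing are assumptions.

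| f | k | Median, full follow-up (months) | Median, censored (months) | Difference |
|---|---|---|---|---|
| 5% | 2 | 4.80 | 4.89 | 0.09 |
| 10% | 2 | 4.66 | 4.83 | 0.17 |
| 20% | 2 | 4.32 | 4.65 | 0.33 |
| 20% | 3 | 3.97 | 4.36 | 0.39 |

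With k = 1 the two medians agree apart from simulation error. The direction matches Step 3 and the size is again modest.

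**The case against.** The strongest reply is that the authors meant withdrawal from treatment. The sentence closes a section on dosing. The same section speaks of patients with a DLT remaining in the study at a given dose, where it plainly means on treatment. Section 5.5 uses withdrawn for patients who stop because of progression, yet Section 7.7 follows those patients. Section 7.7 makes no exception for toxicity delays, asks for contact every 2 to 3 months with patients not seen in clinic, and urges every effort at follow-up. Section 11.3 also appears to keep patients who move to other treatment in the study for follow-up. Data would be lost only if a site put one dosing sentence above all of these. Even then the shift is below one standard error and falls on secondary endpoints.

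Much of this stands. The intent was probably treatment, the loss depends on a literal reading, and the effect is modest. Section 7.8 is a closure rule, so it supports the literal reading only indirectly. None of this removes the conflict. The protocol itself insists that the two kinds of withdrawal differ, so a site may fairly take the phrase in its defined sense, and the synopsis repeats it. That Section 7.7 already plans the follow-up is a reason to align Section 5.7 with it.

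**Conclusion.** The point holds. The delay rule in Section 5.7 and the synopsis is wrong as written and contradicts Sections 4.3.1, 4.3.2 and 7.7.

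The textual conflict is certain; the bias is conditional. It needs sites to apply the sentence literally, delays of this kind to occur, and the affected patients to have excess hazard. In the cases assumed above, the overstatement of 6-month OS runs from zero to 6.3 points, and median PFS moves by 0.09 to 0.39 months in the excess-hazard cases tabulated. The true size cannot be derived from the protocol.

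The primary analyses are largely shielded. The efficacy set contains every dosed patient (Section 8.2). AEs are reported to 28 days after the last dose and followed until resolved or stable (Section 6.3), and an end-of-treatment visit is required (Section 7.6). The correction should be made because lost follow-up cannot be restored and the change costs almost nothing.

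**What to change.** In Section 5.7 and in the synopsis, replace the sentence with: *Patients requiring a dose delay greater than 14 days for DTP3-related toxicity should permanently discontinue DTP3 and remain in the study for follow-up per Sections 7.5 to 7.7.*

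Keep the 14-day treatment rule and the medical monitor route for other delays as they are. The cost is two reworded sentences. No visits are added, because Section 7.7 already plans this follow-up, and the sample size of 24 per cohort is unaffected.

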5.8 Interaction with Other Drugs

The potential of DTP3 to interact with concomitant medication has been studied *in vitro*. DTP3 does not inhibit the cytochrome P450 isoforms, CYP1A2, 2B6, 2C8, 2C9, and 3A4, in human liver microsomes, when tested up to the maximum concentration of 25 μ M. Only a minor time dependant inhibition of CYP3A4 was observed. DTP3 did not induce the cytochrome P450 isoforms, CYP3A4, 2B6 and 1A, in human hepatocytes to a significant degree, when tested at concentrations up to 10 μ M.⁴³

DTP3 was evaluated for its potential to act as a substrate or inhibitor of a range of cell transporters. DTP3 was neither a substrate nor an inhibitor of the majority of transporters evaluated. DTP3 was a substrate for SLC uptake transporters, OAT1B3, MATE-1 and MATE2-K, at 10 μ M, but not at lower concentrations. Some inhibitory potential of DTP3 was noted for MATE1 and MATE2-K, with IC₅₀ values of 11 μ M and >100 μ M, respectively.

Overall, the potential for DTP3-associated drug interaction is considered to be low based on the high IC50 values observed.

5.9 Recommended prophylactic medication/pre-medication

No specific premedication is recommended prior to administration of DTP3, although institution specific policies pertaining to premedication prior to intravenous administration are permitted.

Institution specific prophylaxis policies (e.g. antibiotics, anti-virals, PCP-prophylaxis etc) are permitted.

5.10 COVID19 Vaccination/Testing

Institutional policies for routine COVID19 testing should be followed.

There are **no** protocol limitations to the timing of COVID19 vaccination, relative to initial or subsequent dosing with DTP3, which should be implemented according to the clinical judgement of the investigator.

6. PHARMACOVIGILANCE

6.1 Definitions

Adverse Event (AE): any untoward medical occurrence in a patient administered a medicinal product and which does not necessarily have a causal relationship with this treatment. *An AE can therefore be any unfavourable and unintended sign (including an abnormal laboratory finding), symptom, or disease temporally associated with the use of an investigational medicinal product (IMP), whether or not considered related to the IMP.*

Adverse Reaction (AR): all untoward and unintended responses to an IMP related to any dose administered. All AEs judged by either the reporting Investigator or the medical monitor as having reasonable causal relationship to a medicinal product qualify as adverse reactions. The expression reasonable causal relationship means to convey in general that there is evidence or argument to suggest a causal relationship.

Abnormal laboratory values should only be recorded as AEs if they are judged to be clinically significant by the investigator or delegated sub-investigator. An abnormal value would normally be considered clinically significant if it necessitates any change to the participant's treatment, if it is symptomatic, if it is deemed related to a protocol specified intervention or otherwise at the discretion of the investigator.

Unexpected Adverse Reaction: an AR, the nature or severity of which is not consistent with the applicable product information (*e.g.* investigator's brochure for an unapproved investigational product or summary of product characteristics (SmPC) for an authorised product). When the outcome of the adverse reaction is not consistent with the applicable product information this adverse reaction should be considered as unexpected. Side effects documented in the SmPC which occur in a more severe form than anticipated are also considered to be unexpected.

Serious Adverse Event (SAE) or Serious Adverse Reaction (SAR): any untoward medical occurrence or effect that at any dose:

- Results in death
- Is life-threatening refers to an event in which the patient was at risk of death at the time of the event; it does not refer to an event which hypothetically might have caused death if it were more severe
- Requires hospitalisation, or prolongation of existing inpatients' hospitalisation
- Results in persistent or significant disability or incapacity
- Is a congenital anomaly or birth defect

Medical judgement should be exercised in deciding whether an AE/AR is serious in other situations. Important AE/ARs that are not immediately life-threatening or do not result in death or hospitalisation but may jeopardise the subject or may require intervention to prevent one of the other outcomes listed in the definition above, should also be considered serious.

Suspected Unexpected Serious Adverse Reaction (SUSAR): any suspected adverse reaction related to an IMP that is both unexpected and serious.

6.2 Causality

The assignment of causality should be made by the Investigator responsible for the care of the participant using the definitions in the table below.

In the case of discrepant views on causality between the Investigator and others, all parties will discuss the case. In the event that no agreement is made, the MHRA will be informed of both points of view.

Relationship	Description
Unrelated	There is no evidence of any causal relationship
Unlikely	There is little evidence to suggest there is a causal relationship (e.g. the event did not occur within a reasonable time after administration of the trial medication). There is another reasonable explanation for the event (e.g. the participant's clinical condition, other concomitant treatment).
Possible	There is some evidence to suggest a causal relationship (e.g. because the event occurs within a reasonable time after administration of the trial medication). However, the influence of other factors may have contributed to the event (e.g. the participant's clinical condition, other concomitant treatments).
Probable	There is evidence to suggest a causal relationship and the influence of other factors is unlikely.

Definitely	There is clear evidence to suggest a causal relationship and other possible contributing factors can be ruled out.
Not assessable	There is insufficient or incomplete evidence to make a clinical judgement of the causal relationship.

6.3 Reporting Procedures

All adverse events should be reported during the period from the date of consent to 28 days after the last dose of DTP3. Depending on the nature of the event the reporting procedures below should be followed. Any questions concerning adverse event reporting should be directed to the trial manager in the first instance. A flowchart is given (Safety Reporting Overview) to aid in the reporting procedures. An EDC System will be used for adverse event reporting. Sites will be expected to complete the AE eCRFs using the relevant database and indicating whether it is an SAE or not. SAEs require additional paper reporting. The completed SAE forms should be emailed to the safety reporting inbox (contact details on Safety Reporting Overview), the Trial Manager and CI immediately.

All AEs should be followed up until they have resolved (or stabilised, as some AEs may be ongoing at end of study).

